5.5 Randomisation

Participants will be randomised in a 1:1:2:2:2 ratio to one of five vaccine groups (Table 3).

Randomisation will be performed after informed consent has been documented and eligibility confirmed by the Principal Investigator (PI) or a delegated medically qualified doctor.

Randomisation will be performed using a secure internet-based randomisation system ensuring allocation concealment by a member of the local research team. Masking of group allocation will be applied to participants, clinicians making safety assessments and laboratory staff analysing samples. Staff administering vaccines, collecting blood samples, and performing subsequent study visits will be aware of what they are giving but not involved in subsequent observations or interactions with study subjects.

Table 3 Vaccine groups

Groups	D0	D56	D112
1 **	C19/P	RZV/P	RZV
2	RZV/P	RZV/C19	aQIV or P*
3	aQIV/P	C19/RZV	RZV
4	RZV/aQIV	RZV/P	C19 or P*
5	RZV/P	RZV/aQIV	C19 or P*

P: placebo

**if in winter vaccination season aQIV/ C19 will be given*

***Group 1 will receive aQIV at visit 6 if in winter vaccination season (day 140)*

The allocation will be computer-generated, and randomisation will be stratified by age (50 to 64 years, 65 to 70 years, 71 to 74 years, and 75 years and over) and centre to ensure distribution of age groups between the vaccine groups, by an independent BTC statistician, not involved in the trial, before recruitment begins.

All injections will be administered intramuscularly. When a vaccine is given alongside placebo, the vaccine will be administered in the non-dominant arm. When vaccines are co-administered RZV will be administered into the non-dominant arm and C19 vaccine or aQIV in the dominant arm.

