4.1 Primary outcome

Part A: Assessment of co-administration of COVID-19 and RZV

Co-Primary Endpoints

1) Immunogenicity of C19

Anti-S protein Ig concentrations expressed as Geometric Mean Concentrations (GMCs) for both strains in C19 vaccine/RZV (first or second dose, groups 2 & 3) and C19 vaccine alone (group 1), will be used to calculate between group ratios expressed a geometric mean ratio (GMR), at 1 month after vaccination with C19 vaccine.

2) Immunogenicity of RZV

Anti-gE Ig concentrations expressed as GMCs after co-administration of C19 vaccine/RZV (first or second dose) and RZV alone, 1 month after 2nd dose of RZV, and between-group ratios expressed as GMRs.

Success criteria:

Part A of the trial will be classified as a success if both of the following meet the success criteria:

- 1) The combined administration of C19 vaccine and RZV (first or second dose) will be considered non-inferior to C19 vaccine alone if the lower limit of the 95% confidence interval for the (GMR) of anti-S protein Ig concentrations exceeds 0.67, the standard WHO non-inferiority margin for recommendation of new vaccines.⁷, AND

2) The combined administration of C19 vaccine and RZV (first or second dose) will be considered non-inferior to RZV alone if the lower limit of the 95% confidence interval for the GMR of Anti-gE Ig concentrations exceeds 0.67.

3) Safety of RZV

The rate of grade 3 and 4 solicited systemic adverse reactions (Table 2) after C19 vaccine/RZV (first or second dose, groups 2 and 3) and RZV alone 7 days after vaccination (groups 1-5) This is a descriptive outcome.

Table 2 Solicited AEs collected on post vaccination diary cards

Systemic solicited AEs
Fatigue
Fever
GI symptoms†
Headache
Myalgia
Shivering

†Gastrointestinal symptoms include nausea, vomiting, diarrhoea and/or abdominal pain

Note: The above AEs are assumed to be related and will be classed as adverse reactions.

Part B: Assessment of co-administration of adjuvanted influenza vaccine and RZV

Co-Primary Endpoints

1) Immunogenicity of aQIV

HAI titres expressed as GMCs in aQIV/RZV (first or second dose, groups 4 & 5) and aQIV alone (group 3) will be used to calculate between group ratios, expressed as GMR at one month after aQIV vaccination.

2) Immunogenicity of RZV

Anti-gE Ig concentrations expressed as GMCs after co-administration of aQIV/RZV (first or second dose) and RZV alone, 1 month after 2nd dose of RZV, and between-group ratios expressed as GMRs.

Success criteria:

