5.2 Key design features to minimise bias

Selection/allocation bias will be prevented by concealed randomisation. The allocation will not be revealed until sufficient information to uniquely identify the participant has been entered into the allocation database.

Performance and detection bias will be minimised by blinding participants and clinicians assessing causality to the vaccine received. Laboratory staff analysing samples will be blinded. Laboratory staff who are processing samples only do not need to be blinded. We will also define procedures for follow-up and monitor adherence to the protocol. The participant information leaflet (PIL) and the process of obtaining informed consent will describe the uncertainty about the effects of giving the two vaccines together compared to separately. Therefore, in the event

of inadvertent unblinding of a participant, he or she should not have a strong expectation that one should be better than the other.

Attrition bias will be minimised by using established methods developed in the Coordinating Centre to maximise the quality and completeness of the data (e.g., regular monitoring of data, querying of data in the trial database). Instances of non-adherence will be fully documented and reviewed at trial meetings and an action plan for maximising compliance drawn up as appropriate. Data will be analysed by intention to treat (i.e., according to the treatment allocation, irrespective of future management and events), and every effort will be made to include all randomised patients.

Reporting bias will be minimised by pre-specifying trial outcomes and following a detailed analysis plan which will be prepared in advance of any comparative analyses of the trial data.

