5.6 Blinding

Participants, laboratory staff analysing samples and clinicians assessing causality of AEs will not be informed of the treatment allocation. Staff involved in delivery of the trial treatment and collecting blood samples will be aware of which vaccines/injections a participant is receiving.

Vaccines will be prepared out of sight of the participant and the blind will be maintained by either i) asking participants to look away, ii) masking the syringe with tape and iii) using syringes that as similar as possible. The success of blinding will be assessed using the Bang Blinding Index.

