Diary cards will be reviewed by the local research team daily for 7 days after visit 1 and as required thereafter, and participants may be telephoned by the local research team if any entries are missed and the PI or delegated clinician if there are any concerns about reported symptoms. Participants will be provided with a ruler and thermometer to aid their reporting of AEs. Participants who do not have access to an internet connected device, will have the option to complete a paper diary. Participants will be encouraged to report any symptoms to the local research team and will be contacted by the local research team between day 4-7 to review their diary entries.

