5.8.4 Visit 2: Safety review and blood sampling

At this visit, approximately 4 weeks after visit 1, participants will undergo the following:

- Safety review to assess for any serious adverse events
- Review and reconciliation of diary card data submitted
- Assessment for local and systemic adverse reactions and events and medical history since visit 1
- Provide blood sample for assessment of COVID-19, influenza vaccine immunogenicity
- Provide blood sample for exploratory immunology analysis*
- Participants in group 3 who will not be invited to continue the study will be informed and permission sought to follow up to resolution any clinically significant adverse events after the end of trial participation

5.8.5 Between visit 2 and visit 3

In the period between the second visit and the third visit approximately 4 weeks later participants will be required to:

- Report any hospitalisation as soon as is practically possible using the emergency 24-hour telephone number provided
- Report any other urgent medical concerns using the trial centre emergency procedures
- Report any unsolicited adverse events on the electronic diary card

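### Section 5.5 contradicts itself on whether staff who know the allocation run the follow-up visits, and nothing requires those who handle the diaries behind the co-primary safety endpoint to be blinded

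*Protocol*

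**What the plan says.** **Who knows the allocation.** Section 5.5 gives three aware roles in one sentence: vaccinators, blood collectors and those who perform later visits. It then says that these staff are "performing subsequent study visits will be aware of what they are giving but not involved in subsequent observations or interactions with study subjects". Section 5.6 gives two aware roles: "Staff involved in delivery of the trial treatment and collecting blood samples will be aware of which vaccines/injections a participant is receiving".

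**Who is masked.** Section 5.5 also states: "Masking of group allocation will be applied to participants, clinicians making safety assessments and laboratory staff analysing samples". Section 5.2 rests its claim about bias on a narrower group: "Performance and detection bias will be minimised by blinding participants and clinicians assessing causality to the vaccine received".

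**Who handles the diaries.** Under 5.8.3 the local research team reviews diary cards daily for 7 days after visit 1. The team may telephone about missed entries, and participants "will be contacted by the local research team between day 4-7 to review their diary entries". Visit 2 (5.8.4) includes "Review and reconciliation of diary card data submitted", together with assessment of local and systemic reactions. Visits 4 (5.8.8) and 5 (5.8.10) repeat both tasks. Section 13.5 expects the 7-day diary information to have been reviewed at visit 6 before the safety analysis.

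**The endpoint.** Parts A and B each have the rate of grade 3 and 4 solicited systemic reactions over 7 days after RZV as a co-primary endpoint (4.1). The note to Table 2 says: "The above AEs are assumed to be related and will be classed as adverse reactions". Sections 4.1 and 13.4 make the analysis descriptive.

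**The concern.** Performing a follow-up visit is an interaction with a participant, so the sentence in 5.5 cannot be carried out as written. A site that follows its first half may let aware staff run the visits at which diaries are reconciled. A site that follows its second half may not. Sections 5.5 and 5.6 do not settle which.

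This matters because the named safeguard does not reach the endpoint. Where every solicited systemic event counts as related, a blinded judgement of causality changes nothing. The rate can still be moved by whether an event is recorded, what grade it carries and whether the diary is complete. Systemic grades 2 and 3 in Table 7 are separated by the degree of limitation and the help or treatment needed, which leaves room for judgement. A person who expects more reactions after two vaccines could prompt, query or reconcile differently by group.

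Whether co-administration causes an unacceptable rise in reactogenicity is part of the trial's stated aim (section 3). With no formal test, readers will compare the raw group percentages directly.

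**Working it through.** The protocol gives no expected grade 3 and 4 rate, margin or power for this endpoint, so there is no planned figure to reproduce. The check is a comparison of sections, followed by a count of the diaries concerned.

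**1. Sections side by side**

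| Question | 5.5 | 5.6 | 5.8 and 11 |
|---|---|---|---|
| Vaccinators aware? | Yes | Yes | – |
| Blood collectors aware? | Yes | Yes | – |
| Follow-up-visit staff aware? | Yes, yet with no later contact | Not listed | – |
| Blinded clinical role | Clinicians making safety assessments | Clinicians assessing causality | 11.2: causality by the PI or a delegate not involved in giving vaccines |
| Diary review, calls and reconciliation | Not addressed | Not addressed | Local research team, trial physicians and coordination team, or no role named; blinding not stated |

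**2. Can the local research team include aware people?** Yes. A member of that team performs the randomisation (5.5), and vaccines are given by the clinical care or research team (6.9). Naming the team therefore does not imply blinding.

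**3. Do the visits bring aware people close to the diary work?** Yes. Blood, an aware task under both 5.5 and 5.6, is drawn at visits 2 and 4. Figure 1 makes sampling group-specific: Group 5 gives none at visit 2, Group 4 none at visit 3 and Group 1 none at visit 4. At visit 2 someone must also tell the Group 3 participants who are leaving (5.8.4), and so must know their group. Nothing separates these tasks from reconciliation.

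**4. Does the blinded causality role touch the endpoint?** No, because the note to Table 2 fixes causality in advance.

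**5. Diaries that feed the endpoint.** Only diaries that follow an RZV dose count. The inputs are Table 3 and the group sizes in the synopsis: 120, 120, 240, 240 and 240, with 120 of Group 3 continuing.

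- Visit 1 (Groups 2, 4, 5): 120 + 240 + 240 = 600
- Visit 3 (Groups 1 to 5): 120 + 120 + 120 + 240 + 240 = 840
- Visit 5 (Groups 1, 3): 120 + 120 = 240
- Total: 600 + 840 + 240 = 1,680, which equals 840 participants × 2 doses

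These are planned numbers before dropout. Section 5.8.2 prints 129 continuing Group 3 participants instead of 120. That would give 849 × 2 = 1,698, which makes no practical difference.

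**The case against.** A reader might infer that allocation-aware staff do make the diary calls and reconcile the entries. The protocol does not say so. The calls belong to the local research team, the visit sections name no role, and the sentence in 5.5 itself excludes aware staff from later observations. Drawing blood and reconciling a diary at one visit need not be done by one person. This objection stands: what can be shown is a contradiction and a missing requirement, not a described practice.

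A reader might also infer that causality assessment is the only blinded clinical role. Section 5.5 masks clinicians making safety assessments, which is wider, and 5.7 treats the local PI as blinded. Section 11 has trial physicians and the coordination team review diaries in real time. That helps, but the people who reconcile diaries are not identified as any of the masked clinicians.

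The strongest point is that blinded participants record the timing and severity of their own symptoms (5.8.3). Their direct entries are source data (12.1), fever is measured with a supplied thermometer, and the success of blinding is to be assessed. This limits the route to prompting, follow-up of missed entries and reconciliation. It does not close it: 13.5 waits for data that have been reviewed, checked and completed, and no section says whether the original or the reconciled value is analysed, or whether staff may change a grade.

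Two limits on extent also stand. Counting every diary after every visit (960 + 840 + 840 = 2,640) would overstate the exposure, since only RZV-dose diaries enter the endpoint. The day 4-7 contact may apply only to users of paper diaries: section 11 places it there, while 5.8.3 can be read either way.

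**Conclusion.** The point holds as a contradiction in 5.5, a mismatch with 5.6, and the absence of any blinding requirement for diary review, calls, reconciliation and reaction assessment. The protection claimed in 5.2 rests partly on causality assessment, which does not act on this endpoint. Participant blinding remains.

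Detection bias in the grade 3 and 4 solicited systemic rates therefore cannot be excluded. It could affect about 1,680 planned RZV-dose diaries, if the 120 continuing Group 3 participants in the synopsis is right and dropout is ignored. The documents give no basis for the size or direction of any bias, and any percentage would be invented.

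The consequence is bounded. The safety endpoint is descriptive and lies outside the success criteria of both parts. The immunogenicity criteria are unaffected, because the laboratory staff who analyse samples are blinded. A reading that the trial's success or its immunogenicity conclusions are at risk has no support.

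**What to change.** 1. **Reconcile 5.5 with 5.6.** Delete follow-up-visit staff from the aware roles in 5.5. Vaccinators and blood collectors may stay aware, since group-specific sampling would reveal the group to collectors anyway. The condition is that they, and whoever informs the Group 3 leavers at visit 2, do no diary work.
2. **State who does the diary work.** In 5.8.3, 5.8.4, 5.8.8 and 5.8.10, say that diary review, diary calls, reconciliation, reaction assessment and any change of grade are done by staff without access to the allocation. Apply the same condition to the visit 6 review on which 13.5 relies.
3. **Fix the analysed value.** Use the participant's original 7-day diary entry for the co-primary endpoint. Keep reconciled values as separate, time-stamped fields for sensitivity analysis only.

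The cost is protocol wording, roles on the delegation log and database fields. Section 11.2 already requires an assessor not involved in giving the vaccines, so the second change is mainly a reassignment of tasks. The downside is some loss of rota flexibility at small sites.

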Part B of the trial will be classified as a success if both of the following meet the success criteria:

- 1) The combined administration of aQIV and RZV (first or second dose) will be considered non-inferior to aQIV (for 3 of the strains included in the vaccine; HAI influenza A H3N2, HAI influenza A H1N1 and HAI influenza B Victoria) alone if the lower limit of the 95% confidence interval for the GMR of HAI exceeds 0.67, the standard WHO non-inferiority margin for recommendation of new vaccines.⁷, AND
- 2) The combined administration of aQIV and RZV (first or second dose) will be considered non-inferior to RZV alone if the lower limit of the 95% confidence interval for the GMR of Anti-gE Ig concentrations exceeds 0.67.

3) Safety of RZV

The rate of grade 3 and 4 solicited systemic adverse reactions (Table 2) after aQIV/RZV (first or second dose, groups 4 and 5) and RZV alone 7 days after vaccination (groups 1-5). This is a descriptive outcome.

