11.2 Definitions

Adverse event (AE) is any undesirable event in a subject receiving treatment according to the protocol, including occurrences which are not necessarily caused by or related to administration of the research procedures.

Adverse reaction (AR) is any undesirable experience that has happened to a subject while taking a drug that is suspected to be caused by the drug or drugs.

Serious adverse event (SAE) is any event which results in death, is life threatening, requires hospitalisation or prolongs hospitalisation, results in persistent or significant disability or incapacity, results in abnormal pregnancy outcomes or a congenital anomaly/birth defect in the offspring of a study participant, or any other event which may jeopardise the participant or require intervention to prevent one of the other outcomes listed above

Suspected serious adverse reaction (SSAR) is any serious adverse event that is suspected to be related to the drug or drugs being taken.

Suspected unexpected serious adverse reaction (SUSAR) is an untoward medical occurrence suspected to be related to the drug or drugs being taken that is not consistent with the applicable product information and is serious.

All AEs must be reviewed, and causality must be assessed by the PI or delegated individual not involved in the administration of the trial vaccines (to maintain blinding).

Severity grading for adverse events

The severity of adverse events will be assessed according to scales based on FDA toxicity grading scales for healthy adult volunteers enrolled in preventive vaccine clinical trials, listed in Table 6 and Table 7 below.

Table 6 Severity grading for local adverse events

Adverse Event	Grade	Intensity
Pain at injection site	0	No pain
	1	Pain that is easily tolerated
	2	Pain that interferes with daily activity
	3	Pain that prevents daily activity
	4	A&E visit or hospitalization
Redness at injection site*	0	<2.5 cm
	1	2.5- 5 cm
	2	5.1 - 10 cm
	3	>10 cm
	4	Necrosis or exfoliative dermatitis
Swelling at injection site	0	<2.5cm
	1	2.5 – 5 cm and does not interfere with activity
	2	5.1 - 10 cm or interferes with activity
	3	>10 cm or prevents daily activity
	4	Necrosis

Table 7 Severity grading for systemic adverse events

[figure not shown]
GRADE 0	None
GRADE 1	Mild: Transient or mild discomfort (< 48 hours); No interference with activity; No medical intervention/therapy required

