13.1 Sample size calculation

Sample size calculations have been performed to test all primary immunogenicity objectives in both part A and part B of the trial. All sample size calculations were performed using the SSI module in Stata.⁹

Part A: Assessment of co-administration of COVID-19 vaccine and RZV

We hypothesise that (1) immunogenicity (anti-S protein Ig concentrations, both Original and Omicron strains) of concomitant administration of C19 and RZV (first or second dose) will be non-inferior to C19 alone, and (2) immunogenicity (anti-gE Ig concentrations) of concomitant administration of RZV (first or second dose) and C19 will be non-inferior to RZV alone.

The power calculations to test hypotheses in part A are provided in Table 10.

Table 10 Sample size estimates for part A

Outcome	Sample size excluding 10% inflation for dropout	SD (log10 scale)	Assumed true GMR	Non-inferiority margin (log10 scale)	Power for each outcome	Conjunctive power for part A
Anti-S Ig	95	0.35	1	0.174	92.9%	80.1%
Anti-gE Ig	95	0.35	1	0.174	92.9%	

A sample size of 106 per group will provide 80% power to test all part A hypotheses using a 2.5% one-sided significance level and allowing for 10% dropout.

Part B: Assessment of co-administration of adjuvanted influenza vaccine and RZV

We hypothesise that (1) immunogenicity (for 3 of the strains included in the vaccine; HAI influenza A H3N2, HAI influenza A H1N1 and HAI influenza B Victoria) of concomitant administration of aQIV and RZV (first or second dose) will be non-inferior to aQIV alone, and (2) immunogenicity (anti-gE Ig concentrations) of concomitant administration of RZV (first or second dose) and aQIV will be non-inferior to RZV alone.

The power calculations to test hypotheses in part B are presented in Table 11.

Table 11 Sample size estimates for part B

Outcome	Sample size excluding 10% inflation for dropout	SD (log10 scale)	Assumed true GMR	Non-inferiority margin (log10 scale)	Power for each outcome	Conjunctive power for correlated outcomes (HAI)*	Conjunctive power for part B
HAI influenza A H3N2	216	0.45	1	0.174	98.0%		
HAI influenza A H1N1	216	0.54	1	0.174	91.8%	80.7%	80.6%
HAI influenza B Victoria	216	0.57	1	0.174	88.7%		
Anti-gE Ig	216	0.35	1	0.174	99.93%	-	

* Estimated using correlation matrix from ComFluCOV HAI data; conjunctive power for HAI outcomes was calculated using R.

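### The arm rule in section 5.5 puts C19 and aQIV in one arm when given alone and the other when given with RZV, so injection side is fully aliased with co-administration in the anti-S and HAI co-primary contrasts

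*Protocol*

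**What the plan says.** Protocol section 5.5 gives two rules for the injection arm. For single vaccines: "When a vaccine is given alongside placebo, the vaccine will be administered in the non-dominant arm". For pairs: "When vaccines are co-administered RZV will be administered into the non-dominant arm and C19 vaccine or aQIV in the dominant arm". No reason is given for either.

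Section 4.1 defines the anti-S comparison as "C19 vaccine/RZV (first or second dose, groups 2 & 3) and C19 vaccine alone (group 1"), and the influenza comparison as "HAI titres expressed as GMCs in aQIV/RZV (first or second dose, groups 4 & 5) and aQIV alone (group 3"). Non-inferiority for C19 requires the lower limit of the 95% "confidence interval for the (GMR) of anti-S protein Ig concentrations exceeds 0.67"; for influenza, the lower limit of the 95% "confidence interval for the GMR of HAI exceeds 0.67".

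The synopsis and Table 3 show two injections for every participant vaccinated at day 0 and day 56, and one injection at day 112. The immunogenicity model in section 13.4 contains treatment group, age group, baseline value and centre, with no term for side.

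**The concern.** Randomisation should leave co-administration as the systematic difference between the compared groups. Here the co-vaccine changes arm exactly when RZV is added. If side has any effect on the one-month response to C19 or aQIV, that effect enters the GMR and is read as an effect of co-administration. It could make a harmless combination appear inferior, or conceal a real loss of response; the second is the more serious error in a non-inferiority trial. The design does not force this, because each of these visits already has two injections, one per vaccine or placebo.

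A lesser issue concerns local reactions. Table 6 in section 11.2 grades injection-site pain by its effect on activity (grade 2 is "Pain that interferes with daily activity") and swelling partly so. The same soreness at the C19 or aQIV site could be graded differently in a dominant arm.

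**Working it through.** **1. Arm rule applied to Table 3**

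| Vaccine | Group, day | Given with | Arm under 5.5 |
|---|---|---|---|
| C19 | 1, day 0 | placebo | non-dominant |
| C19 | 2, day 56 | RZV | dominant |
| C19 | 3, day 56 | RZV | dominant |
| aQIV | 3, day 0 | placebo | non-dominant |
| aQIV | 4, day 0 | RZV | dominant |
| aQIV | 5, day 56 | RZV | dominant |

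For both vaccines, two of the four side-by-co-administration cells are empty: alone/dominant and co-administered/non-dominant. Side is a deterministic function of co-administration, so adding a side term would only add a collinear column. This holds whether the two co-administration groups are pooled or compared separately.

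**2. What else differs in each contrast**

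| Contrast | Outcome | Strains | Day of vaccine | Earlier trial vaccine in the co-administration group |
|---|---|---|---|---|
| Group 2 v 1 | anti-S | 2 | 56 v 0 | RZV |
| Group 3 v 1 | anti-S | 2 | 56 v 0 | aQIV |
| Group 4 v 3 | HAI | 3 | 0 v 0 | none |
| Group 5 v 3 | HAI | 3 | 56 v 0 | RZV |

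Taken group by group and strain by strain, this is 2 + 2 + 3 + 3 = 10 comparisons. Seven of them (2 + 2 + 3) also differ in vaccination day and prior trial vaccine. Only the three in Group 4 v 3 do not.

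**3. The protocol's own power figures (section 13.1)**

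Inputs: margin 0.174 on the log10 scale; true GMR 1; sample sizes set "using a 2.5% one-sided significance level and allowing for 10% dropout"; anti-S with 95 per group and SD 0.35; HAI with 216 per group and SDs 0.45, 0.54 and 0.57.

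SE = SD × √(2/n); power = Φ(0.174/SE − 1.96).

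- Anti-S: SE = 0.35 × √(2/95) = 0.0508; Φ(3.426 − 1.96) = 92.9%.
- B/Victoria: SE = 0.57 × √(2/216) = 0.0548; Φ(3.172 − 1.96) = 88.7%.
- H3N2 and H1N1 by the same formula: 98.0% and 91.8%.

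All agree with Tables 10 and 11.

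**4. Illustration under an assumed side effect**

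Let r be the ratio of dominant-arm to non-dominant-arm titre. The documents give no value for r; 0.90 to 1.10 is an assumption.

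Power at a true co-administration GMR of 1 = Φ((0.174 + log10 r)/SE − 1.96).

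One-sided error at a true GMR on the margin = 1 − Φ(1.96 − log10 r/SE).

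| r | Anti-S power | B/Victoria power | Anti-S one-sided error |
|---|---|---|---|
| 0.90 | 71.4% | 64.7% | 0.2% |
| 0.95 | 84.8% | 79.0% | 0.8% |
| 1.00 | 92.9% | 88.7% | 2.5% |
| 1.05 | 97.0% | 94.5% | 6.1% |
| 1.10 | 98.9% | 97.5% | 12.6% |

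Worked example, anti-S, r = 0.90: (0.174 − 0.0458)/0.0508 − 1.96 ≈ 0.565, and Φ(0.565) = 71.4%.

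**5. Anti-gE**

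At days 0 and 56 RZV is in the non-dominant arm both with placebo and with a co-vaccine, so the rule creates no aliasing there. At day 112 Groups 1 and 3 receive RZV as a single injection. That dose is neither given alongside placebo nor co-administered, so 5.5 assigns it no arm.

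**The case against.** The strongest reply is that nothing in the protocol says injection side affects serum antibody one month later. The obvious mechanism, same or opposite arm to earlier doses, concerns side relative to previous vaccination rather than arm dominance. The eligibility criteria ask for documented COVID-19 vaccination but not its side. Any assumed bias put through a power formula yields figures like those above, so they cannot show that the bias exists. This stands. A reader might infer that the anti-S and HAI ratios are biased; the documents support only that they could be, by an unknown amount in an unknown direction.

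Second, correcting the arm rule would not clean up most contrasts, since three of the four also differ in visit day and prior trial vaccine. This stands too. The gain is a clean Group 4 v Group 3 comparison and one fewer alias elsewhere.

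Third, local reactions carry limited weight. The co-primary safety outcome is systemic, safety analysis is descriptive, and the local objective in section 3 compares RZV alone with RZV co-administered. Redness is never graded by activity, so it would be wrong to say that all local grades depend on side. What remains is the secondary outcome in section 4.2 of local events by group, for pain and partly for swelling.

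Fourth, the present rule has a blinding advantage. At day 0 Groups 1, 2, 3 and 5 all have their only active injection in the same arm, so the sore arm does not hint at which vaccine was given. A slot rule loses this for anyone who knows it. The cost is real but small: a contrast of one vaccine with two already tends to show one sore arm against two under either rule.

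**Conclusion.** The aliasing is certain from the text of 5.5 and Table 3. It covers every anti-S and HAI co-primary contrast, and neither the model in section 13.4 nor any later analysis plan can remove it. Its practical weight falls on Group 4 v Group 3, where side is an avoidable difference in the one comparison vaccinated at the same visit.

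The size of any harm is unknown and may be nil. If a dominant-arm titre were 5% or 10% lower, power at the planning sample sizes would fall to 84.8% or 71.4% for anti-S and to 79.0% or 64.7% for B/Victoria. If it were 5% or 10% higher, the one-sided error for anti-S would be about 6.1% or 12.6%. These figures rest wholly on the assumed ratio.

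Two further inferences are not supported. One is that RZV is always in the non-dominant arm: 5.5 is silent on the single day 112 dose. The other is that anti-gE is compromised by this rule: at days 0 and 56 it is not. The protocol's stated power figures are correct for their assumptions and are not in question. This is a design weakness worth correcting because correction is cheap; it does not invalidate the trial.

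**What to change.** Amend 5.5 so that, at days 0 and 56, arm follows vaccine slot in all groups: one arm for RZV or its placebo, the other for C19 or aQIV or their placebo. The sponsor chooses which arm is which, and should also state the arm for the single day 112 injection. For participants already vaccinated under the current rule, report the aliasing as a limit on interpreting the anti-S and HAI ratios.

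The cost is a short change to 5.5 and to the vaccination instructions, with no added injection and no change of dose or timing. If the present co-administration arms are kept, the only change at days 0 and 56 is to the day 0 injections of Groups 1 and 3 (120 + 240 = 360 of the 960 planned participants).

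There are two downsides. Some participants would receive their only active day 0 vaccine in the dominant arm. The sore arm could also hint at vaccine type, so the rule should not be disclosed to participants or to the blinded causality assessors.
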